### **APPENDIX 3. 7-POINT LIKERT SCALE**

The 7-point Likert scale is self-reported by the subject after the context of the scale, described below, is either read to them, or alternatively, it is read by the subjects themselves.

Please take a few moments to think about the symptoms you have had due to your DTH Skin Test in the (specified time period). It is very important for us to get this information. We will be using it as one of the ways to identify the severity of local skin reactions.

According to the scale below, please indicate the severity of erythema, pain, pruritis and swelling following the intradermal injection over the (specified time period).

1. No problem.
2. Minimal problem (can be easily ignored without effort).
3. Mild problem (can be easily ignored with effort).
4. Moderate problem (cannot be ignored but does not influence my daily activities).
5. Moderately severe problem (cannot be ignored and occasionally limits my daily activities).
6. Severe problem (cannot be ignored and often limits my concentration on daily activities).
7. Very severe problem (cannot be ignored and markedly limits my daily activities and often requires rest).

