## **6. TRIAL OBJECTIVES**

### **6.1. Primary Objectives**

The main objectives of the study are to evaluate the safety of intradermally-injected synthesized TNX-2100 SARS-CoV-2 peptide antigens and to assess the presence of DTH reactions in response to intradermal injection of synthesized TNX-2100 SARS-CoV-2 peptide antigens.

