## 7. INVESTIGATIONAL PLAN

### 7.1. Overall Study Design

This is a Proof-of-Concept (POC), dose finding, multi-cohort study designed to evaluate the safety of intradermally-injected synthesized TNX-2100 SARS-CoV-2 peptide antigens and assess the presence of DTH reactions in response to intradermal injection of synthesized TNX-2100 SARS-CoV-2 peptide antigens. This study is to be conducted in a total of approximately 90 subjects (30 subjects per cohort) who are either uninfected/unexposed healthy individuals (Cohort 1), who are confirmed to have recovered from SARS-CoV-2 infection independent of vaccination status (Cohort 2) or who have received a complete SARS-CoV-2 vaccine course with no known history of natural infection (Cohort 3). The study will be conducted at 1-3 investigational sites in the United States.

The study Schedule of Activities will consist of a Baseline/Skin Test Administration at Visit 1 (Day 1) at which time baseline assessments are to be completed, the skin test is performed, and appropriate test samples are collected. Follow-up visits to monitor safety and evaluate the presence or absence of DTH reactions will be conducted per the following schedule: Visit 2 (Day 2); Visit 3 (Day 3); Visit 4 (Day 4); Visit 5 (Day 5). Safety monitoring will continue at Visit 6 (Day 30) and Visit 7 (Day 180) by telephone calls.

Eligible subjects who provide written informed consent and who satisfy eligibility criteria will undergo a nasopharyngeal swab for a polymerase chain reaction (PCR) (reverse transcriptase [RT]-PCR or other) test to detect active SARS-CoV-2 infection. A laboratory PCR test or a sponsor approved rapid PCR test (such as the Accula™ RT-PCR test) may be used. If a laboratory PCR test is used, subjects will complete a Screening Visit between Day -2 and Day -1 to allow processing of the sample prior to the Baseline/Skin Test Administration Visit 1 (Day 1). The rapid PCR test can be performed at Visit 1 (Day 1) and is preferred to facilitate enrolment by reducing the number of required site visits. If the test result is negative, the subject will proceed with the required blood draws followed by intradermal injection of the investigational products (IPs) and controls.

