### **10.4. Administration of the Investigational Products**

In total, each subject will receive 8 intradermal injections (four injections per forearm), spaced two inches apart at pre-determined sites on the volar aspect of the forearms.

The three IPs (TNX-2110, TNX- 2120, TNX-2130) will be administered by intradermal injection (0.1 mL) in two concentration strengths (“1:10 dilution” and “Undiluted”).

Subjects will also receive one intradermal injection of a positive control (CANDIN®), and one intradermal injection (0.1 mL) of a negative control “diluent”. The three IPs (TNX-2110, TNX- 2120, TNX-2130) will be administered by intradermal injection (0.1 mL) in two concentration strengths (“1:10 dilution” and “undiluted”).

Each vial containing IP, diluent, or CANDIN® will be limited to use of one subject. Remaining material will be discarded.

A detailed Pharmacy Manual outlining the IP administration and DTH assessment process will be provided to investigative site staff and is included in [Appendix 5](#). A minimum of 2 members of the investigative site staff will be trained to administer the IPs and controls. Training materials, such as the CDC video for tuberculosis skin testing methodology, will be utilized.

Injections will be administered as shown in [Figure 1](#) in two stages by the order and location illustrated in Table 4. In total, each subject will receive 8 intradermal injections, spaced two inches apart at pre-determined sites on the volar aspect of each forearm. Place injections approximately 3 inches from the antecubital crease.

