**Figure 1 Standardized Intradermal Injection for the TNX-2100 Skin Test**

**Table 4 Administration of In Vivo Investigational Products and Intradermal Controls**

		To be administered in the numerical order shown	
		LEFT arm	RIGHT arm
Stage 1		① Negative control (0.1 mL diluent) IP at 'Diluted' dosea ② TNX-2110 ③ TNX-2120 ④ TNX-2130	⑤ Positive control (0.1 mL CANDIN®)
Safety Monitoring Period			
Stage 2			IP at 'Undiluted' doseb ⑥ TNX-2110 ⑦ TNX-2120 ⑧ TNX-2130
Safety Monitoring Period			

Note: the diluent will consist of phosphate buffer with 0.31% polysorbate 20 and 4.6% mannitol.

a 'Diluted' dose = 0.1 mL (0.025 µg peptide per 100 µL; concentration strength "1:10 dilution")

b 'Undiluted' dose = 0.1 mL (0.25 µg peptide per 100 µL; concentration strength "undiluted")

IP = Investigational Product

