8.1. Disposition of Patients/Subjects

Subject disposition information will be listed. Disposition for all subjects will include tabulations of the number of subjects enrolled, completing, and withdrawing, along with reasons for withdrawal, for each cohort (and overall).

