8.4. Exposure and Compliance

IP exposure and dosing information will be listed for each subject.

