9.1. Adverse Events

Treatment emergent AEs are defined as AEs that either commenced following initiation of study treatment or was present prior to study treatment but increased in frequency or severity following initiation of study treatment. Adverse events of special interest (AESI) include anaphylactic reaction and enhanced disease from repeated exposure to SARS-CoV-2 (in subjects who have recovered from SARS-CoV-2 infection or in subjects recently vaccinated against SARS-CoV-2).

All AEs occurring after completion of the informed consent process and before the end of study, regardless of relationship to study drug, will be included and classified by system organ class (SOC) and preferred term (PT) using the Medical Dictionary for Regulatory Activities (MedDRA) v24.0.

For treatment-emergent AEs (TEAEs), the following will be summarized and presented for the Safety population:

An overall summary of TEAEs, which includes:

- a. the number and percentage of patients experiencing a TEAE
- b. the number and percentage of patients experiencing a TEAE by strongest relationship to IP
- c. the number and percentage of patients experiencing a TEAE by highest severity grade
- d. the number and percentage of patients experiencing a systemic allergic reaction by highest grade according to the World Allergy Organization Grading Scale for Systemic Allergy Reactions
- e. the number and percentage of patients experiencing a treatment emergent SAE (TESAE)
- f. the number and percentage of patients experiencing a TEAE leading to study discontinuation
- g. the number and percentage of patients experiencing a treatment emergent AE of Special Interest

In the overall summary of TEAEs table, besides tabulating the number and percentage of patients, the total number of TEAE episodes will also be provided. If a patient has repeated episodes of a particular TEAE, all episodes will be counted in the summary table.

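### Neither the local-reaction scale nor the SAP identifies site, arm or strength, so no planned summary shows local tolerability of TNX-2100 by strength or apart from the CANDIN control

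*Protocol*

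**What the plan says.** Protocol 6.1 makes safety a main objective: "The main objectives of the study are to evaluate the safety of intradermally-injected synthesized TNX-2100 SARS-CoV-2 peptide antigens". Protocol 7.1 describes the trial in these words: "This is a Proof-of-Concept (POC), dose finding, multi-cohort study designed to evaluate the safety". SAP 2.3 and SAP 10 then remove every efficacy endpoint from the analysis and leave safety alone.

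Protocol 10.4 states: "In total, each subject will receive 8 intradermal injections (four injections per forearm), spaced two inches apart at pre-determined sites". Table 4 numbers the sites. Stage 1 is diluent and the three diluted IPs on the left forearm, and CANDIN on the right. Stage 2, after 60 minutes of observation, is the three undiluted IPs on the right forearm.

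The self-rated scale in Appendix 3 gives this instruction: "please indicate the severity of erythema, pain, pruritis and swelling following the intradermal injection over the (specified time period". It refers to the injection in the singular and has no field for site, arm or strength. Protocol 14.2.4 repeats the wording and sends the reader to Appendix 3 for the details.

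In the SAP:
- Section 9.1 lists local reactions by their 7-point grade. The fields named for the adverse event listing include onset date and time but no site.
- The overall TEAE summary has rows such as "the number and percentage of patients experiencing a TEAE by highest severity grade". No row is by stage, strength, arm or site. Section 7.1.6 counts TEAEs from the first IP injection.
- Section 8.1 plans "tabulations of the number of subjects enrolled, completing, and withdrawing, along with reasons for withdrawal", by cohort. On dosing, section 8.4 says: "IP exposure and dosing information will be listed for each subject".

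Protocol 13.4 had promised more than SAP 8.1 delivers: a summary of discontinuation from treatment as well as from the study.

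**The concern.** The trial gives two strengths of each IP, a tenfold step apart, to the same subject on the same day, alongside a positive control. A local rating says something about a strength only if it can be tied to a site. CANDIN makes this worse. Protocol 10.3 says it is not an IP, Protocol 12.1.10 expects it to react, and it sits on the same forearm as the undiluted IPs. A rating that pools sites will tend to follow the worst one, which may be the control.

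With efficacy dropped, tolerability is the dose-related information left to summarise. As planned, the report will contain no table comparing local reactions at diluted and undiluted sites, or separating either from CANDIN. It will also contain no count, by cohort, of subjects who did not go on to Stage 2.

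**Working it through.** **1. The tenfold step.** Protocol 10.1 gives 2.5 µg/mL per peptide, and Protocol 10.4 gives 0.1 mL per injection. So 2.5 × 0.1 = 0.25 µg undiluted and 0.25/10 = 0.025 µg diluted, which are the figures in Table 4. After Stage 2 the subject has had 0.25 + 0.025 = 0.275 µg per peptide of each IP, 11 times the diluted dose.

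**2. Number of ratings.** Appendix 3 and 14.2.4 name four symptoms. (Protocol 12.1.11 adds tenderness; I count four.) If one rating is given per symptom, each assessment yields 4 ratings. By site group it is 4 × 4 = 16, and by site 4 × 8 = 32. For 90 subjects there are 90 × 8 = 720 injections. Of these, 90 × 6 = 540 are IP, 270 at each strength.

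**3. What pooling can hide.** The documents give no reaction rates, so every rate here is an assumption. Let p be the chance that a site reacts, independent across sites, with 2% at each diluted IP site and 1% at the diluent site.

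- P(any of 8 sites) = 1 − (1 − p_dil)³ (1 − p_und)³ (1 − p_CANDIN)(1 − p_diluent)
- P(any undiluted site) = 1 − (1 − p_und)³

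| CANDIN | Undiluted, per site | Any site (pooled) | Any undiluted site |
|---|---|---|---|
| 10% | 2% | 21.1% | 5.9% |
| 10% | 10% | 38.9% | 27.1% |
| 10% | 20% | 57.1% | 48.8% |
| 30% | 2% | 38.6% | 5.9% |
| 30% | 10% | 52.5% | 27.1% |
| 30% | 20% | 66.6% | 48.8% |
| 50% | 2% | 56.2% | 5.9% |
| 50% | 10% | 66.0% | 27.1% |
| 50% | 20% | 76.1% | 48.8% |

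For example, with CANDIN 50% and undiluted 2%: 1 − 0.98³ × 0.98³ × 0.50 × 0.99 = 56.2%. With CANDIN 10% and undiluted 20%: 1 − 0.98³ × 0.80³ × 0.90 × 0.99 = 57.1%. The pooled rates nearly agree, while the undiluted-site rates differ by 48.8/5.9, about eightfold. At a fixed CANDIN rate the pooled figure does move with the undiluted rate. But without site data the CANDIN rate is not observed, so the pooled figure cannot be unpicked.

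**4. Would a time split do instead?** Stage 1 alone lasts about 60 minutes, and 1/96 is about 1% of the first 96 hours. Protocol 5.3 has the delayed reaction detectable at 18 hours and peaking at 48. Delayed local reactions therefore appear after both strengths have been given, and only a site record can assign them.

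**5. Denominator.** The Safety Population (SAP 6) needs one IP injection. If k of a cohort of 30 do not receive Stage 2, an event rate after Stage 2 taken over all 30 is too low by the factor (30 − k)/30. That is 0.97 for k = 1 and 0.90 for k = 3 (k assumed).

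**The case against.** A reader might infer that the scale takes one rating for all eight injections and that tolerability therefore cannot be read by strength. The documents do not go that far. Appendix 3 never states its unit. Protocol 14.2.4 and SAP 9.1 attach the grade to local adverse events, so one subject may have several. The case report form and the pharmacy manual are not among the documents available, and a site field there cannot be ruled out. Both forearms are photographed, staff inspect the sites and record changes as adverse events, and site location is recorded with induration (Protocol 12.1.10 and 12.1.11). DTH responses are listed by visit (SAP 8.5). All of this stands. These routes are partial and none is tabulated, and CANDIN shares the right arm, so even an arm-level record would not isolate the undiluted IPs.

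A reader might also infer that a subject held at Stage 1 drops out of the disposition table. If followed to the end, that subject counts as completing. The fault is that the table does not separate such a subject from one who received both stages. Listings of dosing and onset times do let a reader find these cases by hand among about 90 subjects.

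Two further points are fair. No objective asks for a comparison of tolerability between strengths; Protocol 6.2 seeks the concentration for a sensitive and specific reaction. And SAP 2.3 speaks of the induration outcome in the past tense, so ratings may already have been collected and a form change could not recover them. The first limits the importance of the point. The second changes the remedy.

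**Conclusion.** The concern holds as a gap in specification and reporting. Neither Appendix 3 and Protocol 14.2.4 nor the SAP specifies site, arm or strength for the self-rated local reactions. No planned table splits local reactions, TEAEs or disposition by stage or strength. Followed as written, the plan yields no summary of local tolerability by strength, or of TNX-2100 apart from its positive control.

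The size depends on reaction rates that the documents do not give. Under the assumptions shown, which include independence between sites, pooling can hide an eightfold difference at the undiluted sites. The conclusion rests on the natural reading of Appendix 3 and on no site field existing in forms not available here. If such a field exists, only the missing tables remain.

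The documents do not support saying that the strength is unrecoverable. Nor would any layout attribute systemic events after Stage 2 to one strength, because by then every subject given Stage 2 has had both.

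**What to change.** 1. **Appendix 3 and Protocol 14.2.4.** Record the four ratings separately for the four site groups in Table 4 (diluent, diluted IPs, CANDIN, undiluted IPs), and record the site with each local adverse event. Cost: 16 short ratings per assessment instead of 4.
2. **SAP 9.1.** Tabulate local reactions by site group and cohort, with both controls shown separately, instead of only listing them. If ratings were already collected without site, use any site recorded with local adverse events, state the limitation in the report, and apply item 1 to the confirmatory study foreseen in Protocol 5.3. Cost: SAP wording and programming.
3. **SAP 8.1.** Tabulate by cohort the number given Stage 1, the number given Stage 2 and the reasons for not proceeding, in line with Protocol 13.4. Use subjects given Stage 2 as the denominator for events after Stage 2. Cost: programming on the dosing data that SAP 8.4 already lists; reasons for not proceeding must be taken from the record if they were captured.

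Splitting TEAEs by onset before or after Stage 2 is optional. Onset times are already listed, so it is cheap, but it describes only the roughly 60-minute Stage 1 window. The report should say that it cannot assign later delayed or systemic events to a strength.

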## APPENDIX 4. CLINICAL CRITERIA FOR DIAGNOSING ANAPHYLAXIS

As detailed by Sampson et al., (2006), anaphylaxis is broadly defined as “a serious allergic reaction that is rapid in onset and may cause death.” Diagnostic criteria defined by the National Institute of Allergy and Infectious Disease/Food Allergy and Anaphylaxis Network during the second symposium on the definition and management of anaphylaxis, modified from Sampson et al. are as follows:

[figure not shown]
Anaphylaxis is highly likely when any of the following three criteria is fulfilled:

1. Acute onset of an illness (minutes to several hours) with involvement of the skin, mucosal tissue, or both (e.g., generalized hives, pruritus or flushing, swollen lips-tongue-uvula) and at least one of the following:
  - a. respiratory compromise (eg, dyspnea, wheeze-bronchospasm, stridor, reduced peak expiratory flow, hypoxemia).
  - b. reduced blood pressure or associated symptoms of end-organ dysfunction (e.g., hypotonia [collapse], syncope, incontinence).
2. Two or more of the following that occur rapidly after exposure to a likely allergen for that subject (minutes to several hours):
  - a. involvement of the skin-mucosal tissue (eg, generalized hives, itch-flush, swollen lips-tongue-uvula)
  - b. respiratory compromise (e.g., dyspnea, wheeze-bronchospasm, stridor, reduced peak expiratory flow, hypoxemia)
  - c. reduced blood pressure or associated symptoms (e.g., hypotonia [collapse], syncope, incontinence)
  - d. persistent gastrointestinal symptoms (e.g., crampy abdominal pain, vomiting).
3. Reduced blood pressure after exposure to known allergen for that subject (minutes to several hours):
  - a. adult: systolic blood pressure <90 mm Hg or >30% decrease from that person’s baseline.

In the event of suspected anaphylaxis or severe hypersensitivity, vital signs, including oxygen saturation and respiration rate, will be measured. Other assessments will be performed at the

discretion of the Investigator. As a precaution, each investigational site should have a resuscitation cart nearby.

CANDIN®	Candida albicans skin test antigen for cellular hypersensitivity
COVID-19	Coronavirus disease 2019
CRF	Case report form
DTH	Delayed-type hypersensitivity
ELISpot	Enzyme-linked immune absorbent spot
FDA	Food and Drug Administration
GCP	Good clinical practices
GLP	Good laboratory practices
ICF	Informed consent
ICH	International Council for Harmonisation
ICS	Intracellular cytokine staining
IP	Investigational product
IRB	Institutional review board
MedDRA	Medical Dictionary for Regulatory Activities
NP	Nasopharyngeal
PBMC	Peripheral blood mononuclear cells
PI	Principal investigator

Abbreviation	Definition
POC	Proof-of-Concept
SAE	Serious adverse event
SAP	Statistical analysis plan
SOC	System Organ Class
SAS	Statistical Analysis System
SARS-CoV-2	Severe acute respiratory syndrome coronavirus 2
Th	T helper cell
TEAE	Treatment-emergent adverse event
WHO	World Health Organization

1. Overview

This statistical analysis plan (SAP) describes the planned analysis and reporting for Tonix Pharmaceuticals, Inc. protocol number TNX-CA-C201 (A Dose Finding Study for the Assessment of Delayed-type Hypersensitivity Reactions to SARS-CoV-2 Peptide Antigens in Uninfected Healthy Subjects, COVID-19 Convalescent Subjects, and COVID-19 Vaccinated Subjects “COVID-19 DTH”), dated 07-Dec-2021, version Final v2.0, amendment 01. Reference materials for this statistical plan include the protocol and the accompanying sample data collection documents. Operational aspects related to collection and timing of planned clinical assessments are not repeated in this SAP unless relevant to the planned analysis.

The structure and content of this SAP provides sufficient detail to meet the requirements identified by the Food and Drug Administration (FDA), European Medicines Agency (EMA), and International Conference on Harmonization (ICH) of Technical Requirements for Registration of Pharmaceuticals for Human Use: Guidance on Statistical Principles in Clinical Trials (ICH, 1998). All work planned and reported for this SAP will follow internationally accepted guidelines, published by the American Statistical Association (ASA, 2018) and the Royal Statistical Society (RSS, 2014), for statistical practice.

The planned analyses identified in this SAP may be included in clinical study reports (CSRs), regulatory submissions, or future manuscripts. Also, post-hoc exploratory analyses not necessarily identified in this SAP may be performed to further examine study data. Any post-hoc or unplanned, exploratory analysis performed will be clearly identified as such in the final CSR.

The final clinical database cannot be locked until the final SAP has been approved and signed.

2. Study Objectives and Endpoints

2.1. Study Objectives

2.1.1. Primary Objective

The main objectives of the study are to evaluate the safety of intradermally-injected synthesized TNX-2100 SARS-Co V-2 peptide antigens and to assess the presence of DTH reactions in response to intradermal injection of synthesized TNX-2100 SARS-Co V-2 peptide antigens.

2.1.2. Secondary Objectives

The secondary objectives are:

- To estimate sensitivity and specificity of test as a marker of active or recovered infection relative to clinical history of infection.
- To identify the optimal synthesized SARS-CoV-2 peptide antigens and concentration for sensitive and specific DTH reaction.
- To identify the optimal timepoint for assessment of the DTH reaction.

- To correlate the DTH reaction with the adaptive T-cell immune response to SARS-CoV-2.

2.2. Study Endpoints

2.2.1. Efficacy Endpoints

2.2.1.1. Primary Efficacy Endpoint

The primary efficacy endpoint of this study is the maximal area of induration ≥ 5 mm at injection sites on the volar aspect of the forearms at 48 hours, 72 hours, and 96 hours post skin test administration.

2.2.1.2. Secondary Efficacy Endpoints

The secondary efficacy endpoints of this study include the following:

- Correlation of DTH reaction to clinical history of prior SARS-CoV-2 infection.
- Correlation of DTH reaction to adaptive T-cell immune response to SARS-CoV-2 assessed by T-Detect COVID Test (Adaptive Biotechnologies).
- Correlation of DTH reaction with in vitro assays of immune response including SARS CoV-2 antibody levels.
- Characterization of Th1 and Th2 responses by measuring cytokine production and cell surface T-cell phenotype markers by intracellular cytokine staining.

